7.4 Study Product Adherence

Adherence with study treatment will be assessed at Visit 2 for monotherapy and Visit 3, Visit 4, and Visit 5 for the combination therapy. The PI must instruct patients to return the medications at each visit. The amount of study medication taken by the patient will be derived by counting the number of tablets in the blister returned and will be recorded in the source document and in the electronic case report form (eCRF).

Adherence to treatment will be estimated by using the below formula:

(number of doses taken during the study)/(number of doses to be taken during the study)×100

A patient who has taken at least 80% and no more than 120% of the required study medication intake since the last visit will be considered as adherent.

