10 WITHDRAWAL CRITERIA

Patients may discontinue the study product, but remain in the study for follow-up, especially for safety and study endpoints (if applicable).

Withdrawal from the study treatment

Withdrawal from the study treatment (monotherapy or extemporaneous combination therapy) refers to any patient who does not receive the complete course, i.e., when no further planned dose is administered from the date of withdrawal. A patient withdrawn from the study treatment may continue further study procedures (safety) planned in the Study Protocol, as deemed appropriate by the Investigator once the safety of the patient is recovered/reassured. A patient's study treatment (monotherapy or extemporaneous combination therapy) may be discontinued for any of the reasons listed below:

- Any AE, which required treatment termination according to the Investigator's judgment.
- Clinically significant intercurrent illness or laboratory results which could compromise the safety of the patient or the scientific value of the study.
- Investigator deems it to be in the best interest of the patient to discontinue.
- Requirement to use prohibited medication that could compromise the safety of the patient or the scientific value of the study.

In addition to the scheduled visits, patients who have been withdrawn from study treatment (monotherapy or extemporaneous combination therapy) may also undergo additional medical follow-up at the discretion of the Investigator.

Withdrawal of patient from the study

The patient may withdraw from the study at any time without explanation, without losing the right to future medical care. The participation of the patient may, at any moment, be terminated by the Investigator, if considered appropriate.

A patient can be withdrawn during the study for any of the following reasons:

- Any AE, which required treatment and study termination for the patient according to the Investigator's judgment.
- Abnormal renal function (creatinine clearance < 30 mL/min) or abnormal liver enzyme parameters (alanine aminotransferase or aspartate aminotransferase level of > 2.5 × upper limit of normal [ULN] or total bilirubin level > 1.5 × ULN) as described in Table 2.
- Patient becomes pregnant during the study.
- Request of the patient (without giving any reason).
- Investigator deems it to be in the best interest of the patient to discontinue.
- Failure to adequately comply with the dosing, evaluations, or other requirements of the study.

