## 15. STUDY MEDICATION ADHERENCE

Adherence with study treatment will be assessed at Visit 2 for monotherapy and Visit 3, Visit 4, and Visit 5 for the combination therapy and it will be presented for the SAF population. A table consisting of summary statistics for percent Adherence along with the number and percent of patients with Adherence in each of the following groups:

Low: percentage of Adherence <80%

Page 26 of 46

Normal: percentage of Adherence =>80% - <=120%

High: percentage of Adherence >120%

For patients who permanently stop the study medication, the "Date of Visit X(n)" will be replaced by the date of study withdrawal.

Adherence to study medication on SAF population for Monotherapy, and SAF population for Combination Therapy. By visit (Visit 2 for monotherapy and Visit 3, Visit 4 and Visit 5) and overall adherence will be produced for Combination Therapy.

A listing of drug accountability will be presented on SAF populations by phase to account for all drug distributed to each patient, including the box number, total number tablets dispensed, returned, consumed, lost (if any), percentage adherence and compliant (yes/no).

A listing of patient continuing the study (eCRF page: Subject Continuation) will be presented for SAF population for Subject's treatment adherence.

- ranging between 80% to 120%?,
- subject tolerate the treatment?,
- subject present uncontrolled BP
- subject continue to the next visit?.

A patient who has taken at least 80% and no more than 120% of the required study medication intake since the last visit will be considered as adherent.

After 4 weeks  $\pm$  2 days in the Assessment period (Week 4), patients BP will be further evaluated at Visit 3: patients with controlled BP levels (sitting BP < 130/80 mmHg in patients < 65 years old/sitting BP < 140/80 mmHg in patients  $\geq$  65 years old) will continue the same extemporaneous combination, while patients with uncontrolled BP levels (sitting BP  $\geq$  130/80 mmHg in patients < 65 years old/sitting BP  $\geq$  140/80 mmHg in patients  $\geq$  65 years old) will be up-titrated from NEB/RAM 5/2.5 mg to NEB/RAM 5/5 mg for further 4 weeks  $\pm$  2 days.

After further 4 weeks  $\pm$  2 days (Week 8) the BP will be assessed again (Visit 4): controlled patients will continue the same extemporaneous combination, while uncontrolled patients:

- if on NEB/RAM 5/2.5 mg, will be up-titrated to NEB/RAM 5/5 mg for further 4 weeks ± 2 days (Visit 5, Week 12);

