#### 15.1. Derivations

Monotherapy and Combination Therapy adherence with study drug based on the drug accountability data will be calculated as the number of doses taken during the study x 100 / number of doses to be taken during the study expressed as a percentage.

For Monotherapy, the expected number of doses to be taken = (Treatment End Date – Treatment Start Date) + 1.

For Combination Therapy, the expected number of doses to be taken = 2 \* ((Treatment End Date - Treatment Start Date) + 1).

For patients who permanently stop the study medication (i.e., monotherapy and/or combination therapy), the expected number of tablets will be calculated up-to the date of study withdrawal.

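### For patients who permanently stop study drug, the SAP counts expected tablets up to study withdrawal, so a patient who took every planned dose may be scored as Low adherence

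*SAP*

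**What the plan says.** SAP 15.1 computes adherence as "the number of doses taken during the study x 100 / number of doses to be taken during the study", the same ratio as in Protocol 7.4 ("number of doses taken during the study)/(number of doses to be taken during the study"). The general denominator follows: "For Monotherapy, the expected number of doses to be taken = (Treatment End Date – Treatment Start Date) + 1", and twice that for combination therapy, where two tablets are taken daily. For patients who permanently stop monotherapy or combination therapy, 15.1 then adds that "the expected number of tablets will be calculated up-to the date of study withdrawal". SAP 15 has a parallel sentence under which the visit date "will be replaced by the date of study withdrawal".

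Results are shown by visit and overall in the Safety population. They are banded, the lowest band being "Low: percentage of Adherence <80" (per cent), and a compliant yes/no entry is listed. A patient counts as adherent under this definition: "A patient who has taken at least 80% and no more than 120% of the required study medication intake since the last visit".

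Protocol 10 has separate headings for withdrawal from treatment and withdrawal from the study. Treatment withdrawal means that no planned dose is given from that date on. Adverse events and the Investigator's judgment are among the listed reasons. On what follows, it says: "A patient withdrawn from the study treatment may continue further study procedures (safety) planned in the Study Protocol".

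**The concern.** Adherence is meant to compare doses taken with doses due. Once treatment has been permanently stopped on the Investigator's decision, no dose is due. Ending the count at study withdrawal puts days without a planned dose into the denominator, which departs from the protocol's own ratio. It also departs from the general formula in the same SAP section if Treatment End Date, which the SAP does not define, means the date of last dose.

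At stake is the meaning of a named secondary endpoint. Protocol 4 justifies measuring adherence by the need to judge efficacy and tolerability better. If a stop for an adverse event appears as Low adherence, tolerability is reported as poor compliance. There is also a gap: a patient who stops drug but completes Visit 5 has no study-withdrawal date, so the programmer would have to choose one.

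**Working it through.** The plan states no numerical result for this derivation, so there is none to reproduce. The check applies the SAP's ratio directly.

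**Inputs.**
- Ratio and both end-date rules: SAP 15.1.
- Low band, below 80%: SAP 15.
- Phase lengths: run-in 4 weeks (28 days), assessment 12 weeks (84 days), Protocol 5.
- Assumption: the patient takes every dose up to the last-dose day *s* of the phase, none afterwards, and leaves the study on day *w*.

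**Formulas.** Let *f* be 1 for monotherapy and 2 for combination.
- General formula, with Treatment End Date read as the last-dose day: 100 × *fs*/(*fs*) = 100%.
- Rule for permanent stoppers: 100 × *fs*/(*fw*) = 100 × *s*/*w*. The factor *f* cancels.

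**Worked patient.** Combination therapy, last dose on day 30, so 2 × 30 = 60 tablets taken.
- Count to last dose: 60/60 = 100%.
- Count to study withdrawal on day 56: 60/(2 × 56) = 60/112 = 53.6%.
- Count to day 84: 60/(2 × 84) = 60/168 = 35.7%. This applies if the patient formally leaves the study on day 84. For a patient who completes Visit 5 it would apply only if the rule were read as running to that visit, which the SAP does not say.

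**Threshold.** With off-drug gap *g* = *w* − *s*, *s*/(*s* + *g*) < 0.80 when *g* > 0.25*s*, which is the same as *g* > 0.20*w*.

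| Study withdrawal on day | Latest stop day scored below 80% | One day later |
|---|---|---|
| 28 | 22 (22/28 = 78.6%) | 23/28 = 82.1% |
| 56 | 44 (44/56 = 78.6%) | 45/56 = 80.4% |
| 84 | 67 (67/84 = 79.8%) | 68/84 = 81.0% |

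**Range with study withdrawal on day 84.** Stop on day 14: 16.7%. Day 28: 33.3%. Day 42: 50.0%. Day 56: 66.7%. Day 80: 95.2%. Each would be 100% with the count ended at the last dose.

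**By visit.** Take last dose on day 26, Visit 3 on day 28 and study withdrawal on day 84. Replacing the Visit 3 date literally by the withdrawal date gives 26/84 = 31.0%. The actual visit date would give 26/28 = 92.9%, and the last-dose date 26/26 = 100%. The visit-date term that SAP 15 replaces appears in no formula in SAP 15.1, so the two sections do not fit together as written.

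**The case against.** The strongest reply is that SAP 15.1 gives a general formula followed by a deliberate exception, and that counting doses after an unapproved stop as missed is a defensible choice. That stands in part. The rule covers every permanent stop, and for a patient who quits on their own initiative a low score carries information. It does not justify the same treatment of a stop ordered by the Investigator, after which Protocol 10 plans no dose. Since Treatment End Date is undefined, the conflict with the general formula is conditional on its meaning the last-dose date; the departure from doses due under Protocol 7.4 is not.

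A second reply is that the gap may usually be short. The SAP takes both the last-medication date (SAP 14) and study discontinuation (SAP 9.1) from the End of Study Treatment form, and Protocol 10 leaves continued procedures to the Investigator. This is possible. The documents give neither the number of such patients nor the length of the gap.

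Third, tolerability is reported elsewhere: SAP 9.1 presents reasons for discontinuation and SAP 18.1.2 tabulates adverse events leading to it. That limits the harm but does not correct the adherence figure.

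A reader might infer that everyone who stops treatment and stays in the study will be scored non-adherent. The documents do not support this. Patients whose gap is at most 20% of the time to withdrawal still score 80% or more, and those who complete Visit 5 have an undefined value rather than a low one.

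A reader might also infer that the rule moves patients out of the Per-Protocol set. No passage makes this percentage a Per-Protocol criterion. SAP 9.2 leaves deviations to case-by-case review, and SAP 5.2 and 5.4 already require Week 12 primary efficacy data, which a patient who left on day 56 would ordinarily lack.

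**Conclusion.** The point holds in this form: as written, the rule can score a patient who took every planned dose as Low, and it gives no defined value for a patient who stops drug and completes the study. Under the assumption of perfect intake until the stop, the score falls below 80% once the off-drug gap exceeds 25% of treated time. The example falls from 100% to 53.6%. How many patients are affected cannot be judged from the documents.

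The consequence is limited to a descriptive secondary endpoint in the Safety population. The primary test does not use this percentage. It should be corrected because the stated rule yields a wrong value and the correction is small.

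**What to change.** In SAP 15 and 15.1, for patients who permanently stop, replace the study-withdrawal date by the date treatment was permanently discontinued, meaning the last planned dose. Define Treatment End Date accordingly, use it for both by-visit and overall figures, and make the two sections refer to the same date. This also settles the case of a patient who stops drug but completes Visit 5. An interval that begins after the stop then has no expected doses and should be shown as not applicable.

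The cost is one sentence in each of two places plus the definition. SAP 14 already takes the last-medication date from the End of Study Treatment form.

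There is one downside. A patient who stops on their own initiative would score as adherent up to the stop, which hides real non-adherence. Either show permanent stops by reason beside the adherence table, using the reasons already collected for disposition, or keep the later doses in the denominator for stops not ordered by the Investigator. In the second case the SAP must say which recorded reasons count as Investigator-ordered and which end date applies to the others, including those who complete Visit 5.

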## 16. EFFICACY OUTCOMES

## 16.1. Primary Efficacy

## 16.1.1. Primary Efficacy Variable(s) & Derivation(s)

The primary efficacy variable is Change in mean sitting SBP between Visit 2 (Week 0) and Visit 5 (Week 12). Blood pressure and pulse measurements will be assessed with the same calibrated automated device, provided by the Sponsor, at each visit.

16.1.2. Intercurrent Event Handling and Data Imputation for Primary Efficacy Variable(s)

Not Applicable.

## 16.1.3. Primary Analysis of Primary Efficacy Variable(s)

The primary objective of this study is to test the hypothesis that

H0: There is no change in the sitting SBP prior or post combination therapy.

H1: There is a difference in the sitting SBP prior or post combination therapy.

The above hypothesis will be tested as following:

Change from baseline in sitting SBP from prior and post combination therapy will be tested using paired t-test. The 2-sided p-value obtained from the paired t-test will be presented.

The primary efficacy analysis will be performed for the mITT population. Site 114 patient data will be removed from the mITT population due to site closure for GCP non-compliance issues. To verify the impact of this exclusion on the study results, the primary efficacy analysis will be conducted both with data from site 114 and without data from site 114.

Page 28 of 46

Assumption of Normality will be investigated using Wilk-Shapiro test. If the p-value is greater than .05, it means we cannot reject the null hypothesis that a variable is normally distributed. If the data is found to be non-Normal, the paired t-test will be replaced by Wilcoxon signed rank test.

The primary endpoint will be summarized descriptively using n, mean, median, SD, Q1, Q3, minimum, and maximum.

Only those patients for whom we have SBP assessment results available at both Baseline (Week 0) and Week 12 will be considered. If baseline (Week 0) SBP value is missing the patient is not included in the mITT population.

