12.2 Determination of Sample Size

A sample size of 215 achieves 90% power to detect a Systolic BP difference of -2.4 mmHg between the null hypothesis mean of 3.0 mmHg and the alternative hypothesis mean of 5.4 mmHg with a known standard deviation of 12.0 mmHg and with a significance level (alpha) of 0.05 using a one-sided one-sample t-test. Such a difference in SBP is highly clinically significant in a population-wide perspective since, as clearly demonstrated by Hardy et al²⁰, if applied nationwide, a hypothetical 1 mmHg shift in SBP among African American and white US populations aged 45 to 64 years was estimated to prevent \approx 9338 incident heart failure events, 6210 incident coronary heart disease events, and 3761 incident stroke events annually, while the hypothetical intervention achieving the larger SBP reduction of 2 mmHg was associated with larger reductions in the incidence of coronary heart disease, stroke, and heart failure for both racial groups.

A total number of 270 patients will be screened considering a screen failure/drop-out rate of 20%, to obtain at least 215 completed patients at the EoS (Visit 5) (patients who complete all visits including EoS Visit [Visit 5]).

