12.5 Statistical Analysis

Descriptive statistics

Patient disposition, demographics and baseline characteristics will be summarized for monotherapy and combination therapy. Medical history will be summarized only for monotherapy. Prior and concomitant medications will be summarized for combination therapy (NEB + RAM).

Continuous variables will be summarized using the number of non-missing observations, mean, SD, minimum, median, and maximum values. Categorical variables will be presented with the number of non-missing observations and column percentages (n, %).

Primary (efficacy) analysis

The primary efficacy analysis will be conducted on the mITT population. The results will be interpreted for the same population.

The primary endpoint is the change in mean sitting SBP between Visit 2 (Week 0) and Visit 5 (Week 12).

The statistical hypothesis will be defined as below:

H0: There is no change in the sitting SBP post combination therapy.

H1: There is a difference in the sitting SBP post combination therapy.

The above hypothesis will be tested as following:

- Change from baseline in sitting SBP from prior and post combination therapy will be tested using paired t-test. The p-value obtained from the paired t-test will be presented.
- Assumption of Normality will be investigated using Wilk-Shapiro test. If the data is found to be non-Normal, the paired t-test will be replaced by Wilcoxon signed rank test.
- The primary endpoint will be summarized descriptively using n, mean, median, SD, Q1 (first quartile), Q3 (third quartile), minimum, and maximum.

MENARIN	Global Medical Department		
	Protocol Template		
Identification Number	Version Number	State	Effective date
FORM-000050125	3.0, CURRENT	Effective	13 May, 2022

Sensitivity analysis

The sensitivity analyses will be conducted using the PP population.

The PP population will be used to assess the robustness of the results obtained using the mITT population.

Secondary (efficacy) analysis

Secondary efficacy variables will be summarized in a descriptive manner using the mITT population.

- Change in mean sitting DBP between Visit 2 (Week 0) and Visit 5 (Week 12).
- Change in mean sitting DBP and SBP between:
 - Visit 2 (Week 0) and Visit 3 (Week 4)
 - Visit 2 (Week 0) and Visit 4 (Week 8)
- Number and proportion of patients achieving the standard BP goal (sitting BP < 140/90 mmHg) at Visit 5 (Week 12).

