#### 6.5. Statistical Tests

The default significant level will be (5%); confidence intervals will be 95% and all tests will be two-sided, unless otherwise specified in the description of the analyses.

Page 20 of 46

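### A Shapiro-Wilk result switches the primary test from the paired t-test to the Wilcoxon signed rank test, so the data decide whether the p-value concerns the mean change or the pseudo-median

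*SAP*

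**What the plan says.** The default primary test is clear. SAP 16.1.3 states "H0: There is no change in the sitting SBP prior or post combination therapy" and, for the paired test, "The 2-sided p-value obtained from the paired t-test will be presented". SAP 6.5 sets the general level: "The default significant level will be (5%); confidence intervals will be 95% and all tests will be two-sided".

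Normality is then tested on the same data. Protocol 12.5 says "Assumption of Normality will be investigated using Wilk-Shapiro test" and gives no threshold. SAP 16.1.3 adds one: "If the p-value is greater than .05, it means we cannot reject the null hypothesis that a variable is normally distributed". Both documents then replace the test when normality is rejected; in the SAP, "If the data is found to be non-Normal, the paired t-test will be replaced by Wilcoxon signed rank test". The reference code in SAP Appendix 1 runs the normality check and the signed rank test on change from baseline.

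The sample size is in terms of means. Protocol 12.2 derives 215 completers from a null mean of 3.0 mmHg, an alternative mean of 5.4 mmHg and an SD of 12.0 mmHg, "using a one-sided one-sample t-test".

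The switch recurs in the secondary and exploratory parts of Protocol 12.5 and in SAP 16.2.1.1, 16.2.1.2, 16.2.1.3 and 16.3.2. SAP 16.4, which brings back the excluded patients from Sites 114 and 507, names only a paired t-test.

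**The concern.** The signed rank test addresses the pseudo-median (the median of all pairwise averages of the change scores). This equals the mean only when the changes are symmetric. Shapiro-Wilk reacts to asymmetry among other departures, so the rule tends to bring in the replacement where it no longer tests the mean. With about 215 patients the t-test for a mean tolerates moderate non-normality, while Shapiro-Wilk has ample power to flag departures that do not matter.

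Two things are at stake. First, under skew the rejection rate for a true zero mean change can leave 5%. Secondly, interpretation suffers. A Wilcoxon p-value could be printed beside a mean change it does not test, and rows for Weeks 4, 8 and 12 could rest on different tests. SAP 16.4 also compares mITT with the all-patients set, and a significant difference triggers re-analysis of all efficacy outcomes. If the mITT result has switched and the other has not, that comparison mixes a change of test with a change of patients.

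**Working it through.** **Step 1. Reproduce the sample size (Protocol 12.2).** Difference 5.4 − 3.0 = 2.4 mmHg, SD 12.0, one-sided alpha 0.05, power 90%.

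n = [12 × (1.645 + 1.282) / 2.4]² = 214.1, rounded up to 215. The noncentral t gives 89.9% power at 215 and needs 216 for 90%, so the stated figure is reproduced. For drop-out, 215 / 0.80 = 268.75, i.e. 269, against 270 planned. The calculation rests on a mean and a t-test; nothing in it refers to a rank test.

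**Step 2. Simulate the planned rule.** N = 215, true mean change 0, 20,000 trials per shape. Each trial ran Shapiro-Wilk at 0.05, then a two-sided t-test if normality was not rejected and a two-sided signed rank test otherwise. The documents give no distribution for the changes, so the shape is an assumption, shown as a range. Skewed shapes are gamma. The mixture has 10% large responders (90% with mean 0 and SD 10, 10% with mean −25 and SD 12, recentred to mean 0).

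| Assumed shape of change | Switch to Wilcoxon | t-test always | Planned rule |
|---|---|---|---|
| Normal | 5% | 5.0% | 5.1% |
| Symmetric, t with 5 df | 84% | 5.2% | 5.0% |
| Symmetric, t with 3 df | 99% | 4.9% | 5.0% |
| Skewness 0.25 | 25% | 5.4% | 6.3% |
| Skewness 0.5 | 75% | 5.0% | 9.1% |
| Skewness 0.75 | 99% | 5.2% | 14.8% |
| Skewness 1.0 | 100% | 5.0% | 22.4% |
| 10% large responders | 94% | 5.0% | 14.6% |

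The Monte Carlo standard error is about 0.15 points at 5% and at most 0.35 points. Separate runs gave 8.3% to 8.8% at skewness 0.5 and 21.1% to 23% at skewness 1.0. The t-test alone was still at 5.5% at skewness 2.0.

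**Step 3. Check the cause.** The standard error of the mean change is 12/√215 = 0.82 mmHg. With true mean 0, the pseudo-median lies about 0.5 mmHg from zero at skewness 0.5 and 1.0 mmHg at skewness 1.0, which is 0.61 and 1.22 standard errors. A two-sided 5% test centred there rejects with probability

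- skewness 0.5: P(Z > 1.96 − 0.61) + P(Z < −1.96 − 0.61) ≈ 8.9% + 0.5% = 9.4%;
- skewness 1.0: P(Z > 1.96 − 1.22) + P(Z < −1.96 − 1.22) ≈ 23.0% + 0.1% = 23.1%.

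These agree with the table. The excess therefore comes from testing a different quantity; the pre-test itself adds little (at skewness 0.5, Wilcoxon used in every trial rejects 9.2%).

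**Step 4. Direction.** With a long tail of large SBP falls and mean change 0, signed rank rejections at skewness 0.5 were 8.7% towards a rise and 0.5% towards a fall; at skewness 1.0, 22.6% and 0.1%.

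**Step 5. At the assumed effect.** A change of 5.4 mmHg is 5.4 / 0.82 = 6.6 standard errors from zero. The t-test has over 99.9% power, and both tests rejected in every simulated trial at skewness 0.5 and 1.0.

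**The case against.** Several stronger readings are tempting, and the documents do not support them.

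- *The test is left open.* It is not. SAP 16.1.3 fixes the trigger, the threshold and both tests, and the code is supplied. The analyst has no discretion; the test depends on the data under a stated rule.
- *A switch loses the mean or its confidence interval.* SAP 16.1.3 summarises the endpoint by mean, SD, median and quartiles whichever test is used. It names no CI for the t-test either, so that gap is not caused by Wilcoxon.
- *The plan has an error rate of 9% or 23%.* Those figures depend on a skewness the documents do not give. Entry of patients uncontrolled at Visit 2 does not create it on its own: with normal true BP and measurement error and a baseline cut at 130 or 140 mmHg, simulated changes had skewness of −0.01 to −0.02 and the rule rejected 4.8% to 5.1%.
- *It inflates false claims of benefit.* With a long tail of large falls the excess points the other way. A false claim of a fall needs a long tail of rises.

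It can also be argued that H0 does not name a mean, that mean sitting SBP may refer only to averaging three readings, and that signed rank is valid if the null is change symmetric about zero. That is correct as far as it goes. However, the default test and the sample size both concern the mean change, and no section says what is being estimated after a switch.

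Mean-based analyses remain elsewhere: the MMRM in SAP 16.1.4, the PP analysis in 16.1.5 and the all-patients analysis in 16.4. They soften the point, but none is the primary mITT test. Even if the switch were read into 16.4, each set would be pre-tested separately, so the tests could still differ.

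**Conclusion.** The point stands in a conditional form. The rule lets a normality test choose the quantity behind the primary p-value, and at N = 215 the t-test does not need that protection. If change scores have skewness of 0.25 to 1.0 (an assumption), a true zero mean change is rejected in about 6% to 23% of trials, against about 5% for the t-test. With normal or symmetric heavy-tailed changes there is no inflation.

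The verdict against zero would rarely change if the true fall is near 5.4 mmHg. The practical harm is in interpretation: a p-value that does not match the mean beside it, and a blurred mITT versus all-patients comparison in SAP 16.4. That is enough to justify the change, but not to say that the trial's conclusion is at risk. The mismatch between the one-sided test against 3.0 mmHg in the sample size and the two-sided test against zero is a separate matter.

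**What to change.** Name the two-sided paired t-test on the mean change, with its 95% CI, as the primary analysis whatever Shapiro-Wilk shows. Report the Wilcoxon signed rank test as a named sensitivity analysis, and keep any normality check as description only. Apply the same rule wherever the paired-test switch appears: Protocol 12.5 (primary, secondary and exploratory parts) and SAP 16.1.3, 16.2.1.1 to 16.2.1.3 and 16.3.2. Keep SAP 16.4 on the same test, so that it differs from the mITT analysis only in the patients included.

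The cost is editing in several sections. Protocol 12.7 makes a change to the primary analysis during the study the subject of a substantial amendment, so one may be needed; SAP v3.0 is dated 17 April 2024 and last patient out was estimated for April 2024, so timing matters. Both tests are already coded in SAP Appendix 1, and N = 215 does not change.
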